Assessing Asthma Symptom Perception: Symptom perception is typically measured in laboratories by self-reported respiratory symptoms while inducing airway constriction with histamine or methacholine.^{78,82,107} However, this approach produces biased data because it generates anxiety and primes patients for certain reactions.^{82,84,107,108} In contrast, measurements in naturalistic settings (e.g., their home), as we propose to do, is a validated method^{87,109} that reduces the emotional threat of the test environment and omits pharmacological techniques and devices that may generate anxiety.⁷⁷

PTSD May Negatively Impact Asthma SMB: Asthma self-management encompasses several complex behaviors such as adherence to controller medications, adequate inhaler technique, use of action plans, allergen avoidance, and avoiding tobacco exposure that are critical for adequate disease control. Adherence to controller medications in particular, is a factor that heavily influences the outcomes of asthmatics.¹¹⁰⁻¹¹² Studies conducted in the general population and our preliminary data from WTC workers shown that only ~50% of patients with asthma adhere to controller therapy or other SMB.^{25-27,113-117}

Mental health conditions are associated with low adherence to chronic disease SMB.¹¹⁸⁻¹²⁰ PTSD, in particular, has been strongly associated with low treatment adherence in multiple chronic diseases.^{21,23,24,121} With smoking being an important part of asthma self-management, it is of special concern that higher rates of smoking have been reported among WTC workers with PTSD.^{122,123} Thus, low adherence to SMB may mediate, in part, the association between PTSD and increased asthma morbidity. However, there is limited data regarding the relationship between PTSD and asthma SMB in the general population or among WTC workers, in particular.

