Power Calculations: We estimated rates of over-perception and asthma morbidity from our prior studies or the literature.^{27,109,154,155,168,229} We adjusted the sample size for the expected correlation of measurements within a participant (interclass correlation coefficient ≥ 0.8).²³⁰ These analyses showed that with 400 patients, the study will have $>90\%$ power to detect a 10% increase in the probability of over-perception in participants with PTSD. We also evaluated the power to identify whether the regression coefficients for the association between the ACQ/AQLQ scores and FEV₁ is different for patients with vs. without PTSD (equivalent to testing an interaction). These analyses showed that with 400 subjects (and 80% retention), the study will have an 82% power to detect a difference of 1 unit between the slopes of patients with and without PTSD.

Aim 3. Assess the relationship between PTSD and adherence to asthma SMB in WTC workers and identify the pathways linking them: Medication adherence analyses will be restricted to patients prescribed controller medications ($>80\%$ of the sample based on prior studies). Primary analyses will use electronic adherence measures; secondary analyses will use MARS scores and other SMB. The univariate association of adherence and PTSD will be assessed using a chi-square test. Multivariable analyses will use a GEE model (logit link function) to control for potential confounders as listed above. We will use similar approaches to assess the associations of potential mediators (over-perception of symptoms, anxiety sensitivity, and illness and medication beliefs, Figure 5) of the relationship between PTSD and medication adherence.

 Mount Sinai	Protocol Title:	Assessing Inflammatory and Behavioral Pathways Linking PTSD to Increased Asthma Morbidity in WTC Workers
	Principal Investigator Name/Contact Info:	[name], DrPH [contact]; [contact]
	Primary Contact Name/Contact Info	[name], MS [contact]; [contact]
	Date Revised:	07/25/16
	Study Number:	IF# 1896970; GCO# 16-0945

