Power Calculation: Power calculations for LGCM were based on published methods.²³⁵ Effect size in this approach is defined as a null and alternative hypothesis value of the RMSEA index, which we hypothesize to be 0.05 (adequate fit) and 0.03 (good exact fit), respectively. Power in SEM can be conceptualized as a function of sample size and the number of parameters to be estimated in the model, relative to the information provided in the overall variance-covariance matrix of the observed variables. The estimated power is based on a proposed sample size of 360 (assuming that 80% of total sample will be on controller medications) with an 80% follow-up rate, yielding estimated power >0.80 for an average effect of 0.10 with an alpha of 0.05. Overall, despite the challenges of estimating *a priori* power for SEM approaches, especially those involving growth models, we believe the proposed study will be adequately powered to address this aim.

We will request a separate IRB approval prior to the intervention phase of the study that is outlined in Aim 4.

Aim 4. Develop and pilot test an integrated intervention for asthma and PTSD by adapting the 3RP, with counseling to promote asthma SMB, and education to correct over-perception of symptoms: **Overview:** Based on the results of Aim 3, we will script messages aimed to counter beliefs linked to low adherence and to support those that promote better asthma SMB; these messages will be incorporated into specific sessions of the 3RP (Appendix D). If Aim 2 shows symptom over-perception in participants with PTSD, we will also integrate strategies to train individuals to more accurately perceive symptoms by providing feedback.⁸⁷ We will conduct a proof-of-concept pilot RCT in a subset of 60 WTC workers with asthma and PTSD who have completed their 12-month study visit to test the enhanced 3RP for PTSD and asthma. We are currently seeking approval for the observational portion of the study only. We will request IRB approval for the interventional (pilot) phase at a later date, in advance of commencing the pilot.

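### Aim 3's only power figure is an RMSEA model-fit calculation; it cannot support power for an undefined effect of 0.10 or for the PTSD-adherence comparison in H3a

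*Combined protocol and SAP*

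**What the plan says.** All of this is in section h), Data Analyses, Aim 3, unless noted.

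- **Hypothesis.** H3a (section 1, Objectives) is that PTSD goes with lower adherence to asthma self-management behaviours (SMB).
- **Analysis.** On medication adherence, "Primary analyses will use electronic adherence measures". Section f) makes that outcome binary, with a threshold of 70% of prescribed days. "The univariate association of adherence and PTSD will be assessed using a chi-square test", followed by a logit-link GEE with confounders. The analysis is restricted to participants prescribed controller medication.
- **Power.** The Aim 3 power paragraph is introduced as a calculation for LGCM. It defines effect size as null and alternative values of RMSEA, "which we hypothesize to be 0.05 (adequate fit) and 0.03 (good exact fit), respectively". The result is reported as "yielding estimated power >0.80 for an average effect of 0.10 with an alpha of 0.05". The number of participants behind that result is printed as 360, explained as the 80% of the sample taking controllers, and retention is put at 80%. The paragraph ends with the view that "we believe the proposed study will be adequately powered to address this aim".
- **Not given.** The paragraph has no model degrees of freedom, scale for the 0.10, PTSD split, adherence rate or within-person correlation for adherence.

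**The concern.** The paragraph moves between three things: a fit-index contrast, an effect of 0.10, and the adequacy of the whole aim. An RMSEA test asks whether the model's covariance structure fits closely enough. Its power is the same whether PTSD lowers adherence by 0, 10 or 20 points, so the first step supports neither of the other two.

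At stake is how H3a will be read. Under an aim-wide assurance of adequate power, a non-significant PTSD-adherence result invites the conclusion that no meaningful deficit exists, while the plan gives no figure for the deficit it could detect.

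**Working it through.** **1. The plan's own figure.** The test compares RMSEA 0.05 (null) with 0.03 (alternative). Under each, the fit statistic is noncentral chi-square with noncentrality λ = (N − 1) × df × RMSEA². The null is rejected below its 5th percentile. Since df is not reported, I scanned it. Power reaches 0.80 only with df of at least 83 (N=360), 99 (N=320), 116 (N=288) or 139 (N=256). A large growth model could have that many, so the figure above 0.80 can be neither confirmed nor refuted. No PTSD effect enters the formula.

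**2. Inputs for H3a.**
- Enrolment is 400 (section c). With 80% on controllers, 400 × 0.80 = 320; with 80% follow-up, 320 × 0.80 = 256. The printed 360 is 90% of 400, so it does not match its own parenthesis. I carry it as an upper case.
- PTSD prevalence is about 30% (Aim 1 power calculations).
- Adherence: the Background reports that "only ~50% of patients with asthma adhere to controller therapy or other SMB". I use 50% for participants without PTSD, which is an assumption because the source figure is an overall rate.
- Alpha is 0.05, taken as two-sided (sidedness is not stated).
- Reading 0.10 as a 10-point difference is also an assumption.

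**3. One-window chi-square, 50% versus 40%.** With n₁ = 0.3N, n₂ = 0.7N and p̄ = 0.3 × 0.40 + 0.7 × 0.50 = 0.47:

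power = Φ[(0.10 − 1.96·SE₀)/SE₁], where SE₀ = √[p̄(1 − p̄)(1/n₁ + 1/n₂)] and SE₁ = √[0.40·0.60/n₁ + 0.50·0.50/n₂].

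At N=256, SE₀ = 0.0681 and SE₁ = 0.0672. Then (0.10 − 0.1334)/0.0672 = −0.497, and Φ(−0.497) = 0.31.

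**4. Three-window GEE.** I multiply the variance by (1 + 2ρ)/3, an exchangeable approximation to a time-averaged comparison with complete data. The plan gives ρ of at least 0.8 for Aim 2 only. The values below are assumptions for adherence.

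| Reading of 0.10 | N=256 | N=320 | N=360 |
|---|---|---|---|
| 10 points, one window | 31% | 37% | 41% |
| 10 points, three windows, ρ = 0.8 | 35% | 42% | 46% |
| 10 points, three windows, ρ = 0.5 | 44% | 52% | 57% |
| 10 points, three windows, ρ = 0.3 | 52% | 62% | 67% |
| Correlation r = 0.10 | 36% | 43% | 47% |

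An unpooled variance adds about one point, which gives the 47% upper end quoted for ρ = 0.8. Using 53% versus 43%, so that the overall rate is 50%, leaves the one-window row unchanged. PTSD prevalence of 25-35% (Background) moves that row to 28-44%. None of this includes confounder adjustment.

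**5. The reading that would succeed.** If 0.10 is f-squared for a single coefficient, noncentrality at N=256 is 256 × 0.10 = 25.6, and Φ(√25.6 − 1.96) = Φ(3.10), above 99%. An R-squared of 0.10 is slightly larger still. Both are much larger effects than r = 0.10, where R-squared is 0.01.

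**6. Detectable difference at 80% power, from 50%.**

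| Analysis | N=320 | N=256 |
|---|---|---|
| One window | 16.9 points | 18.8 points |
| Three windows, ρ = 0.8 | 15.7 | 17.5 |
| Three windows, ρ = 0.5 | 13.9 | 15.4 |
| Three windows, ρ = 0.3 | 12.4 | 13.9 |

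**The case against.** The plan never claims power above 0.80 for the chi-square or GEE test. The paragraph is labelled as an LGCM calculation and admits the difficulty of estimating power for such models. Setting 31% against 80% therefore compares two different tests, and the 10-point reading is mine. This stands: a reader might infer that the plan's printed power is arithmetically wrong, and the documents do not support that. What remains is that the paragraph extends its conclusion to the whole aim.

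The low figures are also not firm bounds. N=256 is pessimistic for the baseline window, which precedes most dropout. With about 320 on controllers and the 95% device return seen in the investigators' prior studies, baseline power is about 36-37%. GEE uses partial follow-up, and lower correlations raise power. Four complete windows with autoregressive correlation 0.3 and N=360 reach 81%. This stands too, so the inference that the study would usually miss a 10-point deficit is not supported under every assumption. But the 81% case needs the unreconciled N, no dropout and a correlation that the plan does not state.

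H3a is broader than binary electronic adherence. It covers inhaler technique and trigger avoidance. Continuous adherence and the self-report scale are secondary, and the LGCM itself includes a PTSD path. True, but none of these has a power figure either, and an RMSEA contrast does not supply one for a path coefficient.

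Finally, a reader might infer that a weak H3a undermines the Aim 4 intervention. The protocol draws those messages from the beliefs most strongly tied to self-management, so the knock-on effect is limited. Nor does the plan say that a non-significant H3a would exclude a 10-point deficit; that is a risk of interpretation.

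**Conclusion.** The concern holds as a gap in support. The RMSEA calculation cannot show power for an effect of 0.10 or for H3a, so the aim-wide assurance is unsupported for the PTSD-adherence comparison. This part rests on the text alone, whatever the 0.10 means.

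The size of the shortfall depends on that meaning. As a 10-point difference, power is about 31-41% for a single window and roughly 35-67% for three windows across correlations of 0.8 to 0.3. As r = 0.10 it is 36-47%. As R-squared or f-squared it exceeds 80%. The 10-point figures assume 50% adherence without PTSD, 30% PTSD, two-sided 0.05 and N between 256 and 360. The LGCM figure itself remains unverified because df is missing.

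**What to change.** 1. Limit the RMSEA statement to overall fit of the growth model, and report the model df.
2. Define the scale of the average effect of 0.10, or delete it.
3. Reconcile the sample size: 80% of 400 is 320 on controllers, and 256 with complete follow-up.
4. Replace the aim-wide adequacy claim with a detectable difference for H3a from the tests to be run. On the reconciled N that is about 17-19 points for one window. For three windows it is about 12-18 points across within-person correlations of 0.3 to 0.8, labelled as an assumption until adherence data give a value.
5. State that a non-significant H3a will be interpreted by its confidence interval against that difference.

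The cost is protocol wording and one short calculation, with no added participants or procedures. The downside is a less favourable stated figure for Aim 3.

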Training and Fidelity: Masters-level clinicians will be trained to deliver the adapted 3RP intervention by [name]. [name] will provide weekly supervision and review audio-taped sessions for treatment fidelity. Pilot RCT Procedures: [name] will adapt the 3RP procedural manual to incorporate new components. We will use data from the 12-month interview to identify WTC workers with asthma and PTSD for the pilot (N=60). Eligible WTC workers who agree to participate will be randomized 1:1 (using adaptive randomization to balance the number of participants in each arm with respect to age, sex and PTSD symptoms severity) to the intervention vs. an attention control group.

Intervention Group: Participants randomized to the adapted 3RP condition will participate in the manualized 8-session group -based program (4-8 participants per group). They will also receive an unblinded AM2 device during the first 6 weeks of the intervention. Attention Control: Control patients will participate in an 8-session group-based program of similar time and therapist attention. The control intervention will consist of educational sessions covering general asthma knowledge (Asthma 1-2-3)²³⁹ group-based support. They will receive blinded AM2 devices.

Outcome Assessment: A telephone follow-up survey 4 weeks after the last session will be administered to assess the patient’s illness and medication beliefs, anxiety sensitivity, their adherence to asthma SMB, and PTSD symptoms. Data Analysis: 1) Quantitative Assessment: Differences in illness (B-IPQ), medication beliefs (BMQ), anxiety sensitivity (ASI-3), adherence to asthma medications (MARS), and PTSD symptoms (PCL) will be assessed using a t-test

 Mount Sinai	Protocol Title:	Assessing Inflammatory and Behavioral Pathways Linking PTSD to Increased Asthma Morbidity in WTC Workers
	Principal Investigator Name/Contact Info:	[name], DrPH [contact]; [contact]
	Primary Contact Name/Contact Info	[name], MS [contact]; [contact]
	Date Revised:	07/25/16
	Study Number:	IF# 1896970; GCO# 16-0945

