or Wilcoxon test, as appropriate. 2) Qualitative Feedback: The post-intervention interview will also include open-ended questions for: a) recollection of specific messages from the counseling, b) satisfaction and perceived usefulness, and c) ways of improving the messages and their delivery. Power: The study will have >80% power to identify a clinically meaningful differences in IPQ, BMQ, ASI, MARS, and PCL scores for 30 patients in each study arm (n=60).

i) Provisions to Monitor the Data to Ensure the Safety of subjects

Data Safety and Monitoring Plan

We have established a monitoring plan for the observational phase of the study (Aims 1-3).

Overview

- A. Brief description of the purpose of the study: The goal of the proposed study is to examine the inflammatory and behavioral mechanisms underlying the association between PTSD and increased asthma morbidity among WTC rescue and recovery workers.
- B. Adherence statement: The Data Safety Monitoring Plan (DSMP) outlined below for the proposed study will adhere to the protocol approved by the MSH and Queens College IRBs.
- C. Data quality and management: Principal investigators will review all data collection forms on an annual basis for completeness and accuracy of the data as well as protocol compliance. A statement reflecting the results of the review will be sent to the NIOSH in the annual report.

Adverse Events

- A. Adverse event grading
 1. Attribution scale: An adverse event is defined as both an expected side effect that is of a serious nature, or an unexpected side effect/event regardless of severity. All events will be graded as to their attribution (unrelated to protocol, or possibly, probably, or definitely related to protocol). Any event that is reported to either a principal investigator or their designated research associates by the subject or medical staff caring for the subject and which meets the criteria will be documented as such.
 2. Expected risks: As detailed in the consent form, the expected risks include:
 - Discomfort caused by personal questions asked in the survey.
 - Distress resulting from the questions related to PTSD or depressive symptoms.
 - Complications of the breathing test which may include dizziness or light-headedness due to deep respirations.

	Protocol Title:	Assessing Inflammatory and Behavioral Pathways Linking PTSD to Increased Asthma Morbidity in WTC Workers
	Principal Investigator Name/Contact Info:	[name], DrPH [contact]; [contact]

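### Both pilot arms are treated in groups, but the Aim 4 test and its >80% power statement make no allowance for correlation within a therapy group

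*Combined protocol and SAP*

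**What the plan says.** All of this is in the Aim 4 text of section h) of the combined protocol and SAP.

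- **Allocation** (Pilot RCT Procedures) is by individual: "Eligible WTC workers who agree to participate will be randomized 1:1".
- **3RP arm** (Intervention Group): eight sessions are delivered to groups, with the size given as "4-8 participants per group".
- **Control arm** (Attention Control): "Control patients will participate in an 8-session group-based program of similar time and therapist attention". No group size is given.
- **Analysis** (Data Analysis): differences in illness beliefs, medication beliefs, anxiety sensitivity, self-reported adherence "and PTSD symptoms (PCL) will be assessed using a t-test" or a Wilcoxon test. There is no term for group or leader.
- **Power claim**, made for 60 participants in two equal arms: "The study will have >80% power to identify a clinically meaningful differences in IPQ, BMQ, ASI, MARS, and PCL scores for 30 patients". No difference, SD, alpha, ICC or design effect accompanies the statement.

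The Aim 2 power paragraph does adjust the sample size for correlation of repeated measurements within a participant. Aim 4 has no comparable adjustment for treatment groups.

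**The concern.** People who sit through eight sessions together share a clinician and a group dynamic. The pilot outcomes (beliefs, anxiety sensitivity, adherence, PTSD symptoms) are ones that such sessions are meant to move, so some correlation within groups is plausible. The t-test and the Wilcoxon test both assume that the 60 scores are independent. With 30 per arm and 4 to 8 per group, the 3RP arm has only 4 to 7 groups, so one unusually strong group or leader can shift the arm mean, and the test would count that shift as evidence for the programme.

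The result is likely to be read inferentially. The plan claims power for between-arm differences on five scales. The DSMB section asks the board to advise on efficacy and lets it recommend stopping for overwhelming benefit.

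**Working it through.** **Inputs from the plan.** 30 per arm; 4 to 8 per group in the 3RP arm; group delivery in both arms; t-test or Wilcoxon test on individuals.

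**Assumptions not in the plan.** Two-sided alpha of 0.05; ICC of 0.01 to 0.10; 5 groups of 6 in each arm as the central case. The control group size of 6 is itself an assumption.

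**1. The plan's own power figure.** It cannot be reproduced, because the difference, SD and alpha are missing. It can only be back-solved. With 30 independent participants per arm, the standard error in SD units is √(2/30) = 0.258. The noncentral t on 58 df needs a multiplier of 2.85 for 80% power, so the detectable difference is 2.85 × 0.258 = 0.74 SD.

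**2. Design effect.** DE = 1 + (m − 1) × ICC. With m = 6:

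- ICC 0.01: DE = 1.05
- ICC 0.05: DE = 1.25
- ICC 0.10: DE = 1.50

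**3. Type I error of the unadjusted t-test.** The test uses a variance that is too small by a factor of about DE, so the true error is roughly 2 × [1 − Φ(1.96/√DE)]. If only the 3RP arm is clustered, the factor is (1 + DE)/2.

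| ICC | Both arms: formula | Both arms: simulated | 3RP arm only: formula | 3RP arm only: simulated |
|---|---|---|---|---|
| 0.01 | 5.6% | 5.8% | 5.3% | 5.3% |
| 0.05 | 8.0% | 8.0% | 6.5% | 6.5% |
| 0.10 | 11.0% | 11.2% | 8.0% | 7.9% |

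Across group sizes from 4 to 8, with both arms clustered, the simulated error runs from 6.6% to 9.2% at ICC 0.05 and from 8.4% to 13.3% at ICC 0.10.

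**4. Detectable difference when the analysis respects the groups.** Five groups per arm leave 2 × (5 − 1) = 8 df for the arm comparison. The multiplier for 80% power on 8 df is 3.20, and the detectable difference is 3.20 × √(2 × DE/30).

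- ICC 0.05: 3.20 × 0.289 = 0.92 SD
- ICC 0.10: 3.20 × 0.316 = 1.01 SD

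On the same basis, power for a difference of 0.74 SD is 61% at ICC 0.05 and 53% at ICC 0.10.

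Dividing 30 by DE and keeping individual-level df would give smaller detectable differences. That ignores how few groups there are, and it does not match an analysis that uses group-based df.

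**The case against.** The strongest reply is that this is a proof-of-concept pilot with no declared primary endpoint. It is deferred to a separate IRB submission, and a DSMB that includes a biostatistician will review its protocol beforehand. All of that is in the documents and it limits the consequence. It does not change the analysis that is written down.

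The ICC is also unknown. At 0.01 the error is under 6%, which matters little. This stands: the inflation is conditional on the ICC, and the documents give no value.

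Three stronger readings are tempting, and the documents do not support them.

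- **That the >80% is overstated.** A reader might infer this from the missing design effect. Without the difference, SD and alpha it cannot be shown. If the clinically meaningful differences exceed about 0.92 SD (ICC 0.05) or 1.01 SD (ICC 0.10), the claim survives in the 5-groups-of-6 case.
- **That both arms run in groups of 4 to 8.** The size is given for the 3RP arm only. If the control arm carried no clustering, the inflation would be milder, as the right-hand columns of the table show. Since control is also group-based, those columns are a lower bound for the same 3RP group size and ICC.
- **That allocation must also balance site and language for groups to be formed.** The study has two sites and enrols English and Spanish speakers, but the Aim 4 text does not say where the pilot sessions are held or in which languages. A delivery failure cannot be derived from that.

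**Conclusion.** The point holds in a limited form. Both arms are group-delivered, the planned tests treat participants as independent, and nothing in the Aim 4 text corrects for this. For any within-group ICC above 0 the p-values will be too small. In the central case the nominal 5% becomes about 6% to 11% over an assumed ICC of 0.01 to 0.10, or about 5% to 8% if clustering were confined to the 3RP arm. These figures rest on an assumed ICC, assumed groups of 6 and a two-sided alpha of 0.05.

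The power statement is unsupported rather than shown to be wrong: its inputs are absent, and it states no allowance for grouping. The matter should be corrected before the pilot is submitted for approval. It has no bearing on Aims 1 to 3.

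**What to change.** In the Aim 4 text:

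1. **Procedures.** State the control group size. Record a therapy-group ID and a leader ID for every pilot participant.
2. **Data Analysis.** Replace the t-test/Wilcoxon comparison with a linear mixed model that has arm as a fixed effect, a random effect for therapy group, and Kenward-Roger or Satterthwaite degrees of freedom. A t-test on group means is a simpler alternative.
3. **Power.** Replace the sentence with a detectable difference, and state the assumed ICC, alpha and group size, with df based on the number of groups. For example: with 5 groups of 6 per arm and two-sided alpha 0.05, 80% power for about 0.92 SD at ICC 0.05 and 1.01 SD at ICC 0.10, compared with 0.74 SD if participants were independent.

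The cost is two ID variables and revised wording, with no extra participants or staff. The real price is wider uncertainty and a less favourable power statement. Even at an ICC of 0, planning on 8 df gives 3.20 × 0.258 = 0.83 SD. With so few groups the between-group variance will also be poorly estimated, so the pilot should be presented mainly as estimation.
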